3 ABBREVIATIONS

Table 1 Abbreviations

ADE	Adverse Device Effect
AE	Adverse Event
AFE	Analog Front End
ARD	Absolute Relative Difference
BMI	Body Mass Index
CFR	Code of Federal Regulations
CGM	Continuous Glucose Monitor/Monitoring
CRF	Case Report Form
DKA	Diabetic Ketoacidosis
EDC	Electronic Data Capture
FDA	Food and Drug Administration
GCP	Good Clinical Practice
HbA1c	Glycosylated Hemoglobin
HIV	Human Immunodeficiency Virus
ICH	International Conference on Harmonisation
IDE	Investigational Device Exemption
IRB	Institutional Review Board
ISO	International Organization for Standardization
IIT	Intensive Insulin Therapy
IMU	Inertial Measurement Unit
IV	Intra Venous
LA	Laboratory Analyzer
MARD	Mean Absolute Relative Difference
mg/dL	Milligrams per deciliter
NFC	Near Field Communication
NIIT	Non-Intensive Insulin Therapy
OCT	Optical Coherence Tomography
PCB	Printed Circuit Board
PI	Principal Investigator
POC	Point of Care
QA	Quality Assurance
QC	Quality Control
SAE	Serious Adverse Event
SAP	Statistical Analysis Plan
SMBG	Self-Monitoring Blood Glucose
SOA	Schedule of Activities
YSI	YSI 2300 STAT PLUS Analyzer
UADE	Unanticipated Adverse Device Effect
US	United States

4 PROTOCOL SYNOPSIS

Table 2 Protocol Synopsis

Title:	Safety and Effectiveness Study of the BioliniQ MicroArray Intradermal Continuous Glucose Biowearable System
Study Sponsor:	BioliniQ, Incorporated
Investigational Device:	BioliniQ System: BioliniQ MicroArray Intradermal Continuous Glucose Biowearable System.
Reference Device:	FDA-cleared Laboratory Analyzer (LA) [YSI STAT PLUS 2300 Glucose and L-Lactate Analyzer (Yellow Springs, Ohio)]
Comparator Devices:	
The following commercially available comparator devices will be used to collect glucose data for reference analysis:
 
• Self-monitoring blood glucose (SMBG) meter: [REDACTED]• Continuous Glucose Monitor (CGM): [REDACTED] [REDACTED]
Design:	Clinical safety and effectiveness study – open label, prospective, multi-center, single arm
Objectives:	The primary objective of the study is to evaluate the safety and effectiveness of the BioliniQ MicroArray Intradermal Continuous Glucose Biowearable System, which is intended to be worn for up to five (5) days (up to 120 hours) in adults with diabetes mellitus (DM). Data collected from this study is intended to be used to support commercial marketing application(s) for the intended commercial patient population of non-insulin-users.
Study Population	To attain sufficient hypoglycemic and hyperglycemic values in the study in conjunction and ensure that underrepresented populations are included in the evaluation, the study will enroll subjects outside the device's intended population and include persons requiring insulin for management of their disease. [REDACTED]
Number of Subjects:	Enroll up to 247 subjects to ensure at least 206 subjects are treated allowing for up to 18.2% screen failures.

Number of Centers:	A minimum of five (5) and up to eight (8) centers in the United States will participate in the study.
Estimated Duration:	
Randomization	The study will utilize three (3) independent randomization assignments with 1:1 ratio for the location of the biowearable (left vs. right volar forearm), 7:3 ratio for the number of biowearables (one vs. two), and the 1:1 ratio for the primary biowearable determination (proximal vs. distal) for subjects who were randomized to wear two biowearables.
Co-Primary Endpoints:	
1. For all available matched pair data points when the Biowearable displays BLUE ("in target" color indicator), the percentage of reference blood glucose values between 55-207 mg/dL must be calculated, [REDACTED]2. For all available matched pair points when the Biowearable displays YELLOW ("above target" color indicator), the percentage of reference blood glucose values between 154-460 mg/dL must be calculated, [REDACTED] 
[REDACTED]

Safety Analyses:	
1. Overall adverse device effect rate2. Individual adverse device effect rates3. Distribution of Draize assessments for erythema and edema for BioliniQ Biowearable
Observational Analyses:	[REDACTED]
Device Precision:	Precision of the BioliniQ Biowearables from subjects who wore two biowearables will be assessed [REDACTED]

Sample Size Statistical Rationale:	[REDACTED]
Inclusion Criteria:	
Individuals may be included in the study if they satisfy all the following:
 
General
 
1. ≥ 22 years old.2. Willing and able to provide written signed and dated informed consent.3. Access to phone or computer with internet to complete subject log. 
Diabetes History and Health
 
4. Diagnosis of type 1 diabetes (T1D)/ LADA or type 2 diabetes (T2D) and on intensive insulin therapy (IIT) with known dosing parameters for at least three (3) months prior to the Screening Visit with an A1c of 5.5%-10% or diagnosis of type 2 diabetes (T2D) and on non-intensive insulin therapy (NIIT) or T2D not using insulin with an A1c of 7.5% to 11%.5. Weigh at least 110 lbs (50 kilograms).6. Be otherwise in good health, as determined by a medical care professional.7. Willing to refrain from Acetaminophen use for the duration of study enrollment.8. If using an automated insulin delivery (AID) system, willing to disable automated features and go into open loop mode during the duration of in-clinic days. 
Device and Glucose Assessments – Willing to:
 
9. Wear one (1) commercial CGM system [REDACTED] on the abdomen per approved labeling and have up to 1 replacement.10. Wear up to two (2) BiolinQ Biowearables simultaneously following the application procedures on the volar forearm for up to 7 days.11. Participate in two (2) In-Clinic sessions lasting up to 11.5 hours of blood draws (anticipated up to 13 hours on site per visit) each.12. Perform up to five (5) fingersticks a day with the SMBG device provided during non-in-clinic days.13. Avoid immersing study devices into water (e.g., no hot tub, SCUBA diving).14. Wear an activity tracker or record activity levels on a daily log.

Exclusion Criteria:	
Individuals with any of the following will be excluded:
 
General
 
1. Current participation in another investigational study protocol. (If a subject has recently completed participation in another drug study, the subject must have completed that study at least 30 days prior to being enrolled in this study.) Note: Subjects will not be excluded if enrolled in another observational trial, wherein the subject is in the follow-up phase and no tests/procedures impacting the subject's health are required. Subjects will be excluded if they have been previously enrolled in this study.2. Work for, are family members with, or live with someone that works for the sponsor or competitor diabetes-related company (includes social media influencers or bloggers).3. In the investigator's opinion, any reason that may lead to subject non-compliance with study requirements or confound study data. 
Health
 
4. Currently taking Hydroxyurea.5. Known allergy to medical grade adhesives, acrylic, latex, or isopropyl alcohol.6. Have dermatological conditions that preclude wearing BioliniQ Biowearables (e.g., extensive psoriasis, recent burns, severe sunburn, extensive eczema, extensive scarring, dermatitis herpetiformis, skin lesions, erythema, infection, or other conditions at the discretion of the investigator).7. For subjects of child-bearing potential, pregnant or not practicing an acceptable form of birth control during the study.8. Hematocrit measurement via point-of-care (POC) or laboratory testing that is less than the applicable below-mentioned value:
a. Male: 36.0%b. Female: 33.0%9. Have donated blood, had significant blood loss, or participated in a study with significant blood sampling (340 cc or more) within 56 days prior to study enrollment or plan to participate in such activities during study wear.10. Required or scheduled to have diathermy, X-ray, MRI, or CT during study wear.11. In the investigator's opinion, the subject has a history of concomitant medical condition that could interfere with the study participation or present a risk to the safety and welfare of the subject or study staff. Such historical conditions include but are not limited to:
a. Syncope in past 6 monthsb. Severe hypoglycemia (loss of consciousness, seizure, or emergency medical technician assistance within the past 6 months)c. Diabetic ketoacidosis (DKA) requiring hospital admission in the past 6 monthsd. Coagulopathye. Chronic infectious disease (e.g., HIV/AIDS, Hepatitis B or C)f. End stage renal disease and currently managed by dialysis or anticipating initiating dialysis during the study wear periodg. History of congestive heart failure
----------------------------	--

Methodology:	This is an open label, single arm, multi-center study conducted in 5-8 investigational sites in the United States. Enroll up to 247 subjects to yield at least 206 treated subjects assuming up to 18.2 % screen failures.
Consent and Screening:	Subjects are considered enrolled after signing and dating an Institutional Review Board (IRB) approved informed consent form (ICF). activities must be completed within 30 days prior to the Bioliniq application and include eligibility criteria, vitals, demographics, medical history review, Fitzpatrick Skin assessment, pregnancy testing (as applicable), A1c and hematocrit tests. Subjects who meet the study eligibility criteria will be scheduled for Bioliniq Biowearable application. Screen failures must exit the study and reasons for exit are documented. Subjects who do not complete screening activities within 30 days are still eligible to participate in the study but must be reconsented and re-screened.
Subjects who passed the screening activities will be randomized	[REDACTED]

[figure not shown]
The YSI STAT PLUS 2300 Glucose and L-Lactate Analyzer will be used to measure glucose values (reference data) for all blood draws during in-clinic sessions. Four active venous blood draws will be done every hour (one blood draw every 15 ± 7 minutes). A matching SMBG fingerstick on the same arm as the BioliniQ Biowearable will be taken simultaneously with the draw for three (3) out of every four (4) blood draws for comparative purposes.

[figure not shown]
Using glucose measurements taken under close direction and observation of the investigator staff, insulin dosing (for subjects on insulin) and meal composition/timing may be manipulated during the in-clinic session to obtain sufficient data variation between 40-400 mg/dL and attain sample sizes required for performance evaluation to support device commercial application.

[figure not shown]
Investigators or designated staff will monitor subjects for safety during an in-clinic session. In-Clinic Guidelines (Appendix 1 – In-Clinic Guidelines) will be provided as guidance, but the investigator or designee will maintain final discretion for any in-clinic procedures and methods used based on their medical expertise and training. A “crash cart” will be prepared and easily accessible for potential emergency situations. At a minimum, this cart should include vial(s) of insulin, normal saline, blood pressure cuff, defibrillator, a bag-valve mask, carbohydrate snacks, glucose tabs or gel, glucagon, and dextrose solutions. Subjects will be discharged at the end of the in-clinic day according to investigator discretion per Appendix 1 – In-Clinic Guidelines.

Adverse Event, Protocol Deviation and Device Observation Assessments:

After consent and through study exit, each subject will be monitored for any new onset and/or worsening of adverse events regardless of the relatedness to the investigational device, procedure, protocol deviations, or device observations. Adverse events will be followed through resolution. If the investigator deemed the event is stable and requires no additional

	
follow-up, then the subject may exit the study. Protocol Deviations and Device Observations will be documented and reported as applicable.
 
Study Exit:
 
Subjects may exit the study after screen failure, if all devices fail prior to end of wear period, or at subject completion of protocol after device removal and resolution of any ongoing adverse events. Subjects lost-to-follow-up may exit after at least three (3) attempts to contact the subject have been documented. Subjects may also exit study at any time with their withdrawal of consent or an investigator decision to withdraw the subject for cause. Reason for study exit for each subject must be documented.

Sponsor and Contact Information:	
BioliniQ, Incorporated [name]
 

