11.4 DEVICE PRECISION

Randomization for 30% of subjects treated will receive a second Biolinq Biowearable to analyze device precision. Randomization scheme will ensure equally weighted assignments obtained from all participating clinical sites.

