14.3 ENROLLMENT

Subjects who sign the IRB approved ICF will be considered “Enrolled” in this study.

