17.1.1 ENROLLED COHORT

The Enrolled Cohort includes all subjects who sign the study IRB approved informed consent. Analyses pertaining to screening eligibility, safety, and protocol compliance prior to the Bioliniq application, and study exit will be performed using the Enrolled Cohort.

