17.1.2 TREATED COHORT (ANALYSIS POPULATION)

All enrolled subjects who have undergone device application will be included in all analyses. All data that is collected during the study will be included in the analysis.

[figure not shown]

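### At the stated 18.2% screen-failure allowance, the cap of 247 enrolled yields about 202 treated subjects, 4 short of the stated minimum of 206

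*Combined protocol and SAP*

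**What the plan says.** The three figures appear twice in section 4 (Protocol Synopsis) of the combined protocol and SAP. The Number of Subjects row says "Enroll up to 247 subjects to ensure at least 206 subjects are treated allowing for up to 18.2% screen failures". The Methodology row says "Enroll up to 247 subjects to yield at least 206 treated subjects assuming up to 18.2 % screen failures". The number 247 is a ceiling, 206 a floor, and 18.2% the largest screen-failure rate provided for. Neither row says what 18.2% is a percentage of.

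Other sections fix the terms:

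- **Enrolled** means consented. Section 14.3: "Subjects who sign the IRB approved ICF will be considered" enrolled. Section 17.1.1: "The Enrolled Cohort includes all subjects who sign the study IRB approved informed consent".
- **Screen failures** occur after consent. Consent and Screening, section 4: "Screen failures must exit the study and reasons for exit are documented".
- **Treated** means that a device was applied. Section 17.1.2, which defines the analysis population: "All enrolled subjects who have undergone device application will be included in all analyses".

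The sample-size rationale in the synopsis is redacted, so the origin of the three numbers cannot be seen.

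**The concern.** Because enrolment is counted at consent, every screen failure uses up one of the 247 places. The plan therefore has to produce its treated minimum from 247 less the failures. At the highest failure rate it says it can absorb, it does not: the ceiling is reached before the floor. The sponsor would then have to accept fewer treated subjects than it has stated or enrol beyond its own cap. The words "to ensure at least 206 subjects are treated" promise more than the numbers deliver.

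The treated subjects are the analysis population, so 206 is the planned size of the main analysis. No visible success rule depends on 206, and with the rationale redacted no statement about power is possible. What is at stake is the internal consistency of a stated sample-size figure.

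**Working it through.** **Inputs (section 4, Number of Subjects and Methodology rows).** Cap on enrolment E = 247; minimum treated T = 206; screen-failure allowance d = 0.182. It is assumed that every subject who passes screening has a device applied; any other loss before application would widen the gap.

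**1. Can 247 be reproduced from 206 and 18.2%?**

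- Rate as a share of those consented: T/(1 − d) = 206/0.818 = 251.8, so 252.
- Rate as a share of those treated: T × (1 + d) = 206 × 1.182 = 243.5, so 244.

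Neither gives 247. Rounding of the rate does not explain this: 18.15% gives 206/0.8185 = 251.7 and 18.25% gives 206/0.8175 = 252.0, so the first formula always leads to 252.

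**2. Treated subjects expected from the cap.** E × (1 − d) = 247 × 0.818 = 202.05, about 202. The shortfall is 206 − 202 = 4, and 4/206 = 1.9%.

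**3. What each pair of figures implies about the third.**

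| Kept | Implied third figure (share of consented) | Stated |
|---|---|---|
| 247 and 206 | rate 41/247 = 16.6% | 18.2% |
| 206 and 18.2% | cap 252 (252 × 0.818 = 206.1; 251 × 0.818 = 205.3) | 247 |
| 247 and 18.2% | treated 202 (202/0.818 = 246.9, so 247) | 206 |

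The third row shows that 247 and 18.2% fit each other at 202 treated: 45 failures in 247 is 18.2%. The pair 247 and 206 corresponds to 41/206 = 19.9% of treated, so 18.2% does not describe that pair on either denominator.

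**4. The alternative reading.** If 18.2% is a share of treated subjects, 247/1.182 = 209 treated, which is above 206. The sentence is then true, with 3 consents to spare (247 − 244).

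**5. How often the floor would be met.** If each consented subject independently fails screening with probability 0.182, the chance of at least 206 treated out of 247 is about 29%. With 252 consents it is about 55%, since 252 reaches 206 only on average.

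**6. Visible consequence.** Section 11.4 says "Randomization for 30% of subjects treated will receive a second Biolinq Biowearable to analyze device precision". Thirty per cent of 206 is 61.8 and of 202 is 60.6, so about 62 becomes about 61 subjects with two wearables.

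**The case against.** The strongest reply is that the contradiction depends on a denominator the text never states. Read as a share of treated subjects, 18.2% requires 244 consents, and both halves of the sentence hold. Nor is it decisive that this reading does not reproduce 247, because 247 is a cap and need not be an exact product. This stands as a reason for caution about which figure is at fault. It does not remove the point: a screen-failure rate ordinarily means a share of those screened, the protocol counts enrolment at consent, and a reader applying those definitions gets 202.

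The second reply is that the consequence is slight, and that is correct. The co-primary endpoints are percentages of matched sensor–reference pairs, not of subjects. With four draws an hour over two sessions of up to 11.5 hours, a subject gives up to 4 × 11.5 × 2 = 92 draws, so about 18,600 draws from 202 subjects against about 18,950 from 206. If interval width scales with the square root of the number of subjects, the intervals widen by a factor of √(206/202) = 1.01, about 1%.

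Third, the shortfall is conditional. The 18.2% is an upper allowance, no expected rate is given, and at 16.6% or less the floor is met. That also stands, but the plan claims to be covered up to 18.2%, and it is at that limit that the claim fails.

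Finally, rewriting the rate as 16.6% merely to make the arithmetic close would back-fit a planning assumption. That is a fair criticism, and it limits when that correction should be used.

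**Conclusion.** The concern holds. On the ordinary meaning of a screen-failure rate, the enrolment cap, the treated minimum and the allowance cannot all be right. At 18.2% the cap gives about 202 treated subjects, 4 (1.9%) below the stated minimum. Put another way, the allowance is 1.6 percentage points too high for the other two figures, or the cap is 5 consents too low.

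This rests on two assumptions: that the rate is a share of consented subjects, and that all who pass screening receive a device. If the rate was meant as a share of treated subjects, there is no shortfall, only an unstated denominator. It is a minor inconsistency that should be corrected, and it is not evidence that the study is underpowered. The visible text does not show which of the three numbers is wrong.

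**What to change.** The sponsor should state the denominator of the screen-failure rate, reconcile the three figures with the unredacted sample-size rationale, and make the same correction in the Number of Subjects and Methodology rows of section 4. The choice depends on which figures are firm:

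- **247 and 206 are firm:** restate the allowance as up to 16.6% (41 of 247), provided that is a realistic planning rate and not chosen only to make the figures agree. No extra subjects.
- **247 and 18.2% are firm:** restate the treated minimum as 202 and confirm that the rationale still holds at 202. No extra subjects; one check of the rationale.
- **206 and 18.2% are firm:** raise the cap to 252. This allows up to 5 more consents and screenings, and gives 206 on average only.
- **18.2% was meant as a share of treated subjects:** say so in both rows; no number has to change.

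Each option is a short wording change in two places. The first two and the last leave the enrolment cap where it is.

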5 SCHEMA

6 SCHEDULE OF ACTIVITIES (SOA)

7 INTRODUCTION

There are 27 million people in the US with Type 2 diabetes on non-insulin therapies and three million with Type 2 diabetes requiring basal insulin only.^{1,2,3} At a population level, glycemic control in people with diabetes has worsened over the past 10-15 years despite the introduction of six new drug therapeutic categories, as published in the New England Journal of Medicine.⁴ Recent studies have demonstrated CGM's effectiveness in people with Type 2 diabetes, including those not using insulin,^{5,6,7} and the American Diabetes Association recommends CGM use in persons with Type 2 diabetes. ADA recommends intermittent use of CGM to aid in evaluating periods of hyperglycemia to make medication dose adjustments.⁸ Despite these recommendations, less than 1% of the Type 2 non-insulin using population are estimated to be using conventional CGM. Commonly cited barriers to conventional CGM adoption for all diabetes populations include cost, discomfort/pain on insertion, skin/adhesive problems, size/form factor, disruptive alerts, and difficulty interpreting CGM data.^{9,10}

The absence of a device specifically designed to support disease management for people with Type 2 diabetes leaves these individuals with inadequate options to improve metabolic health. Currently, people with Type 2 diabetes are required to make the choice between using CGMs designed and optimized for people with Type 1 diabetes or continuing to rely on discrete blood glucose measurements produced by test strips. These blood glucose measurements can be painful and inconvenient to use and provide limited context on personal health trends and patterns, including the impact of food, medications, and activity on glycemic variability. Given the rising rates of Type 2 diabetes and prediabetes globally, as well as the increased risk for diabetes diagnoses following COVID-19 infection, there is a clear and growing need for more accessible, less invasive, and easier-to-use CGM devices designed specifically for people with Type 2 diabetes.

The primary objective of the study is to evaluate the safety and effectiveness of the Biolinq MicroArray Intradermal Continuous Glucose Biowearable System over a 5-day period in adults with diabetes mellitus. Data collected from this study is intended to be used to support commercial marketing application(s) for the intended commercial patient population of non-insulin-users.

8 STUDY MATERIALS

8.1 BIOLINQ MICROARRAY INTRADERMAL CONTINUOUS GLUCOSE BIOWEARABLE SYSTEM

The reportable glucose range for the sensor is between 70 mg/dL and 400 mg/dL. BLINQ does not provide glucose information below 70 mg/dL to mitigate the risk of off-label use by those who need more information about hypoglycemia, such as persons requiring multiple daily insulin injections. Additionally, the device does not have any audible or vibratory alerts or alarms.

[figure not shown]
A summary of clinical studies conducted by Biolinq with the current version Biolinq MicroArray Intradermal Continuous Glucose System is provided in a Report of Prior Investigations.

